## 16.4 Ethical considerations

### 16.4.1 Risk benefit assessment

No risk for participants is associated with the proteome sub-study as it only entails laboratory assessments of samples collected during the SaDAPT trial/ART initiation cohort and linking it to anonymized clinical data collected as part of the SaDAPT trial/ART initiation cohort. Samples will be labelled with the participant number while the participant identification log will remain with the site investigators during the study and at the SolidarMed archive in Lesotho after the termination of the study activities at the sites, thus all assessments for the proteome sub-study will be fully anonymous. No human genome analysis will be performed.

Predicting active TB in high-risk patients such as PLHIV remains woefully inadequate. Current tests (interferon release assays, transcriptional signatures) are complicated to perform, expensive and display underwhelming diagnostic accuracy. A protein based diagnostic signature for prediction of TB and/or IRIS paves the way for a simple, cheap point of care test.

## 1. Administrative information

### Revision history

Version	Date	Who	Comments
0.1	30 May 2024	[name]	First draft
0.2	20 June 2024	[name]	Revised to include feedback from core SaDAPT team plus to add estimand framework.
0.3	24 June 2024	[name]	Revised to incorporate feedback of team and receive estimand input from external reviewer.
1.0	27 June 2024	[name]	Incorporates all feedback of team and estimand input from external reviewer. For signature.
1.1	13 January 2025	[name]	Corrects small inconsistencies. Clarifies the detection limit used for the primary analysis for devices in Malawi with higher VL detection limit than 400 copies/mL.
2.0	14 January 2025	[name]	For signature.

## Abbreviations

AE	Adverse event
AESI	Adverse event of special interest
AIDS	Acquired immunodeficiency syndrome
ART	Antiretroviral therapy
CNS	Central nervous system
CrAg	Cryptococcal antigen
CRF	Case report form
DBS	Dried blood spot
HIV	Human immunodeficiency virus
ICH	International Council on Harmonisation of Technical Requirements for Registration of Pharmaceuticals for Human Use
IRIS	Immune reconstitution inflammatory syndrome
ITT	Intention to treat (analysis population)
PLHIV	People living with HIV
PP	Per protocol
RCT	Randomized controlled trial
REDCap	Research Electronic Data Capture
SAE	Serious adverse event
SDI	Same-day initiation
Swiss TPH	Swiss Tropical and Public Health Institute
TB	Tuberculosis
TPT	TB preventive treatment
VL	Viral load
WHO	World health organization
W4SS	WHO four-symptom screening

## Data management and sharing

Data are captured by study staff directly into an electronic RedCap database, hosted at University of Basel. Data export is done regularly by the study data manager. Queries are raised by the data management, statistics, and monitoring teams and resolved by the site teams.

Key trial data will be made available just before publication of the main manuscript through an appropriate data repository such as Zenodo, and will be referenced accordingly in the main manuscript.

## 2. Introduction

### 2.1 Background and rationale

HIV remains a major cause of morbidity and premature death in many sub-Saharan African countries including Lesotho and Malawi. The most important opportunistic infection associated with HIV is TB, accounting for over 200'000 HIV-related deaths worldwide, mainly in low-income settings, where prevalence of HIV/TB-coinfection is highest.

An important approach to improve access to ART—and thereby reduce HIV transmission as well as AIDS related morbidity and mortality—is the implementation of rapid, and if possible same-day initiation (SDI) of ART. PLHIV with opportunistic infections are at risk of developing immune reconstitution inflammatory syndrome (IRIS) after initiation of ART. Until the release of a guideline update in 2021, WHO had recommended to delay initiation of ART in case of presumptive TB until TB has been investigated and TB treatment initiated if TB disease has been confirmed in order to reduce the risk of IRIS. The 2021 guideline update contains for the first time a “clinical consideration” to start ART in PLHIV with presumptive TB but no signs of central nervous system (CNS) disease while rapidly investigating for TB, thus allowing SDI for this subgroup of PLHIV. The guidelines emphasize the need for further research on the impact of SDI in PLHIV with presumptive TB on various health outcomes including mortality, HIV and TB outcomes, retention in care, adverse events and IRIS.

### 2.2 Objectives

To compare two approaches for the timing of ART initiation in PLHIV with presumptive TB but no signs of CNS disease (“ART first” versus “TB results first”) with regard to HIV viral suppression, engagement in care, serious adverse events (SAEs) and adverse events (AEs) consistent with TB-IRIS (AEs of special interest, AESIs) in a randomized trial reflecting routine primary and secondary care setting in Lesotho and Malawi .

**Primary objective:** To assess if same-day ART initiation (“ART first”) is non-inferior to rapid ART initiation (“TB results first”) with regard to HIV viral suppression (VL <400 copies/mL) 26 weeks after enrolment among PLHIV with presumptive TB

**Secondary objectives:** To compare in PLHIV with presumptive TB same-day ART initiation (“ART first”) versus rapid ART initiation (“TB results first”) with regard to:

- retention in care
- disengagement from care
- unsuppressed VL
- safety outcomes (SAEs, and AESIs)
- TB incidence
- proportion of PLHIV with rapid ART initiation (within 7 and within 28 days)

**Exploratory objectives:**

- To describe the prevalence of TB disease at enrolment

- To assess potential sociodemographic and clinical risk factors for adverse outcomes after same day or rapid ART initiation
- To assess HIV phylogenetics and resistance at enrolment

### 3. Study methods

#### 3.1 Trial design

This is an open-label, two country, two-arm, parallel-group 1:1 individually randomized controlled trial, conducted in Lesotho (7 facilities) and Blantyre district of Malawi (4 facilities). Full details of the trial design are available in the published protocol (2).

#### Trial population

Participants were recruited among individuals presenting at one of the study clinics. Routine staff of all study clinics were asked to identify individuals, 12 years or older, testing HIV-positive or known to be HIV-positive and not taking ART to the trial's site investigator. The site investigator then screened potentially eligible individuals based on the below-mentioned inclusion and exclusion criteria and approach them for consent.

Inclusion criteria are:

- 12 years or older
- HIV-positive
- Not taking ART (naïve or reported no ART intake since 90 days or more)
- Presenting with one or more TB symptoms according to WHO four-symptom screening (4WSS: reported cough, fever, weight loss, night sweats)
- Planning to continue care at the study facility for at least 30 weeks
- Consent (age 18 years or older) or assent and guardian consent (age 12 - 17 years)

Exclusion criteria are:

- Medical condition requiring admission or referral to a higher level health facility at enrolment
- Symptoms or clinical signs suggestive for diseases of the central nervous system (CNS)
- Positive cryptococcal antigen test (CrAg)
- Reporting to be pregnant (pregnancy test not required)
- Taking TB treatment or TB preventive therapy (TPT)

#### Trial procedures

Participants were consecutively enrolled and randomized in the ratio 1:1. Participants were recruited among individuals presenting at one of the primary and secondary level study clinics. All participants provided written informed consent. Enrolled participants received a clinical evaluation including an interview and physical examination, and laboratory tests, in particular diagnostic tests for TB. A follow-up study visit is expected to be done 26 weeks after enrolment. Further details are provided in the protocol (2).

## Trial arms

The two arms of the trial are in brief:

“ART first” arm:

- Offer of ART initiation on the day of enrolment independent of TB investigations

“TB results first” arm:

- Offer of ART initiation only after active TB has been refuted or confirmed

Further information about procedures for the trial arms can be found in the protocol (2).

## Endpoints

As per the protocol, the primary endpoint of the trial is:

- HIV viral suppression <400 copies/mL 26 (22 – 40) weeks after enrolment (obtained from routine laboratory reports at study facility, from laboratory reports of referral facility in case of transfer out, or from dried blood spot (DBS) sample for participants without documented clinic visit but found during home visit tracing)

As per the protocol, the secondary endpoints of the trial are:

- Retention in care 26 (22 – 30) weeks after enrolment, defined as a documented ART clinic visit between 22 and 30 weeks after enrolment
- Engagement in care 26 (22 – 30) weeks after enrolment, defined as reporting regular ART intake, irrespective if a documented visit took place between 22 and 30 weeks after enrolment
- Disengagement from care 26 (22 – 30) weeks after enrolment, defined as non-engaged in care but reached through patient tracing
- Lost to follow-up 26 (22 – 30) weeks after enrolment, defined as non-retained in care and not reached through tracing
- Non-traumatic mortality, SAEs, and AESIs (see section 7.1.3 for definition) during the first 30 weeks after enrolment
- Incidence of TB disease (microbiologically confirmed and/or clinical diagnosis) during the first 30 weeks after enrolment, defined as any TB diagnosis after enrolment not classified as prevalent TB at enrolment (see definition below under exploratory endpoints)
- HIV viral suppression at 26 (22 – 40) weeks using different thresholds (<20 copies/mL; <100 copies/mL; <1000 copies/mL)
- ART initiation within 7 and within 28 days after enrolment

As per the protocol, the exploratory endpoints of the trial are:

- Clinical characteristics of participants with non-traumatic hospitalizations and deaths in PLHIV with presumptive TB
- Prevalence of active TB diagnosed at enrolment, defined as TB diagnosed clinically or microbiologically through the TB investigations initiated at enrolment and completed up to a maximum of 28 days after enrolment.

### 3.2 Randomization

Participants were randomly allocated to trial arms at the time of enrolment. Randomization was stratified by country (Malawi and Lesotho) with randomly varying block sizes (details on block sizes held by the trial statistician). The randomization lists were generated by computer by an independent statistician not involved in the trial and uploaded to the study database. Allocation was revealed to the study staff electronically on the study tablet. Study staff then informed routine staff about arm allocation.

### 3.3 Sample size

As per the protocol: The sample size has been calculated with regard to the primary endpoint of the study. Secondary endpoints were not considered for the determination of the sample size. The expected proportion with viral suppression at 26 weeks after enrolment in the “TB results first” arm is 75%.

To test the hypothesis of non-inferiority of the primary outcome between the two arms, we set the non-inferiority margin to 10%, the power to 80%, and a one-sided alpha level of 0.025. These assumptions yield a sample size of 295 participants per arm.

If participants were found to be ineligible post-randomization and before recruitment ended (primarily for TB investigations happening prior to enrolment), they were replaced in order to reach the required sample size of 295 eligible participants per arm. Additional participants found to be ineligible after randomization will be excluded without replacement. Female participants becoming pregnant after enrolment will not be excluded.

### 3.4 Framework

The primary endpoint comparison between the two arms is non-inferiority. If the intervention arm (ART first) is found to be non-inferior to the control (TB results first), in both the ITT and per-protocol population, then we will assess for superiority (see section 6.2).

### 3.5 Statistical interim analyses and stopping guidance

A data safety monitoring board (DSMB) was set up with the purpose to protect the safety of study participants, to assist and advise the SaDAPT steering committee to protect the integrity, validity and credibility of the trial. The main task of the DSMB is to review SAEs and AESIs. Based on the review of SAEs and AESIs, the DSMB members shall flag concerns regarding safety and give recommendations to the SaDAPT Steering Committee whether to continue, amend or halt the trial due to these concerns. The trial protocol does not foresee any interim analysis or interim review of outcome data. Further details are provided in the DSMB charter.

### 3.6 Timing of final analysis

Once the last participant has reached the endpoint or 40 weeks have passed since their randomization, the data will be cleaned. Once the database is considered complete, it

will be locked. The locked database will be stored at the Division of Clinical Epidemiology at the University Hospital Basel.

### 3.7 Timing of outcome assessments

Baseline is defined as the date of randomization. Time will be measured from randomization.

Baseline laboratory results are defined as those measured at the time of screening to a maximum of 14 days after screening. Of note, the time of a laboratory result is defined as the time when the sample was taken, not the time when the sample was processed or result available. Any laboratory tests done to establish a TB diagnosis and completed within 28 days of enrolment are considered for the establishment of prevalent TB.

Table 2 shows the nominal activity weeks and the permitted ranges as defined in the protocol, and as defined for analysis. The analysis windows are chosen to be as inclusive (wide) as possible while retaining clinical relevance, and without overlap between the windows for different activities. For the primary outcome and secondary outcomes of viral load, if there is more than one measurement recorded within the allowed time window, then any evidence of viral suppression within the window will be considered. For all other measurements and outcomes, if there is more than one measurement within a given interval, then the value will be taken that is within the protocol defined window but closest to the nominal activity day.

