Study Intervention:	
“ART first” arm:
 
 
- ART initiation on the day of enrolment independent of TB investigations
 
 
“TB results first” arm:
 
 
- ART initiation only after active TB has been refuted or confirmed
 

Number of Participants with Rationale:	
Based on the assumptions of non-inferiority of the primary outcome between the two arms, proportions of viral suppression at 26 weeks of 75% in both arms and selection of a non-inferiority margin of 10%, a power of 80%, and a one-sided alpha level of 0.025, a sample size of 590 participants will be required.

Study Duration:	First participant in: October 2022. Expected recruitment period to reach sample size: 18 months. Follow-up duration: maximum 40 weeks. Last participant out: December 2024.
Study Centre(s):	Seven primary or secondary health care facilities in Lesotho and four primary health care facilities in Blantyre district, Malawi.
Statistical Considerations:	We will perform a non-inferiority comparison between the arms on the primary outcome of viral suppression at 26 weeks. Under the assumptions of the sample size calculation, the proportion of viral suppression in the “TB results first” arm is expected to be 75% and the non-inferiority margin is set at 10%. For analysis, we will use a confidence interval approach. We will do the comparison using both a per-protocol (PP) and a modified intent-to-treat (mITT) population. If the lower bound of the 95% confidence interval for the risk difference excludes -10% in both the PP and mITT population, then the intervention will be considered non-inferior. If the “ART first” arm is found to be non-inferior to the “TB results first” arm, then we will assess for superiority using the mITT set.
GCP Statement:	This study will be conducted in compliance with the protocol, the current version of the Declaration of Helsinki, the ICH-GCP as well as all national legal and regulatory requirements.

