#### **6.4.2 “ART first” arm**

The study staff will instruct routine staff to offer same-day ART, independent of completion of TB assessment.

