### **6.6 TB test results review, (routine staff)**

The following procedures are expected to be conducted by routine care providers within one week after enrolment. The study staff will not intervene at this moment.

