### Primary outcome analysis

The primary analysis for this study will be the comparison of viral suppression rates between the two study arms. For the primary outcome, we will summarize the numbers and percentages of participants included in the analysis, and experiencing the intercurrent events, as per Tables 2a and 2b.

The analysis will use a modified Poisson regression with a log link and robust standard errors to calculate risk differences (10,11). The model will be adjusted for country, the pre-specified randomization stratification factor. (12) Moreover, we will adjust for the most important baseline characteristics (age, gender, CD4 cell count, and ART status) if found to be unbalanced between study arms. In the case of convergence issues, we will use marginal standardization to obtain the risk differences (13).

For the non-inferiority comparison between the two arms, a CI approach will be used. A figure illustrating the confidence intervals for the risk differences and the non-inferiority margin will be presented. If the lower bound of the confidence interval for the risk difference does not include the non-inferiority margin, then the intervention will be considered non-inferior.

For the non-inferiority comparison in the per-protocol analysis, we will use weighting techniques to re-weight the population (14) to account for a potential lack of exchangeability introduced by excluding individuals where the offer of ART did not follow the intervention strategy.

In addition to the absolute effect measure of risk differences, we will report the relative effect of the intervention as well with odds ratios and risk ratios as recommended by the CONSORTs statement (6).

As per section 3.4, if the intervention is found to be non-inferior to the control arm in both the ITT and per-protocol population, then we will assess for superiority under the superiority comparison approach (Table 2a) by assessing whether the 95% CI for the risk difference excludes 0.

We will conduct a complete case analysis in which only individuals with a valid VL measurement in the endpoint window of 22 to 30 weeks is included.

We will summarize what proportion of the primary outcome information came from tracing activities.

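### The 14-day window for baseline laboratory samples allows a post-randomisation CD4 count, on ART more often in the ART-first arm, to enter the primary model as a baseline covariate; probably a small effect, and cheap to close

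*SAP*

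**What the plan says.** SAP 3.7 (Timing of outcome assessments) contains two rules that do not agree. It says "Baseline is defined as the date of randomization". It then says "Baseline laboratory results are defined as those measured at the time of screening to a maximum of 14 days after screening". The 14 days cannot be read as an allowance for slow reporting, because the same paragraph says "the time of a laboratory result is defined as the time when the sample was taken, not the time when the sample was processed". No condition ties the sample to the first ART dose.

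The arms differ in when ART starts. For the ART-first arm, SAP 3.1 (Trial arms) has "Offer of ART initiation on the day of enrolment independent of TB investigations", and Protocol 6.4.2 has "The study staff will instruct routine staff to offer same-day ART, independent of completion of TB assessment". In the TB-results-first arm, ART is deferred until the TB work-up is available (Protocol 6.4.1). The review of those results is "expected to be conducted by routine care providers within one week after enrolment" (Protocol 6.6). ART may also start on day 0 in that arm if TB is diagnosed that day.

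The primary model in SAP 6.2 is adjusted for country, and also for "baseline characteristics (age, gender, CD4 cell count, and ART status) if found to be unbalanced between study arms". SAP 5.5 has the steering committee judge imbalance by eye before seeing outcome data, with a stated leaning toward including covariates. CD4 is also a row in the SAP 8.2 baseline table. The protocol's own list of conditional covariates (9.2.1) does not contain CD4; the SAP added it.

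**The concern.** A baseline covariate should not be open to influence by the allocated treatment. Timing of ART is what this trial randomises. If the only CD4 for a participant is drawn on, say, day 10, the time that person has spent on ART depends on the arm. The recorded variable would then measure something slightly different in each arm.

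Two things could follow. The baseline table could show a CD4 difference that randomisation did not produce. That difference, or an ordinary chance imbalance, could also lead the committee to add CD4 to the primary model, and the model would then remove a small part of a treatment effect as if it were a baseline difference. In addition, a late CD4 exists only for people who returned within 14 days, which is itself a post-randomisation event.

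**Working it through.** **The plan's own figure.** With 75% suppression in both arms, a 10-point margin, one-sided alpha 0.025 and 80% power, n per arm = (1.960 + 0.842)² × 2 × 0.75 × 0.25 / 0.10² = 294.3, rounded up to 295, or 590 in total. This matches Protocol 9.1 and SAP 3.3. Power at 295 per arm is 80.1%. The point does not change the sample size.

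**Does any other rule exclude a late sample?** SAP 3.7 takes the value closest to the nominal day, but only where there is more than one measurement. SAP Table 1 has no baseline row. A single late CD4 therefore passes.

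**Size.** The documents give none of the three inputs needed, so all are assumptions:

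- f: share of ART-first participants whose baseline CD4 is on ART, minus the same share in the TB-results-first arm (2% to 50%)
- g: CD4 gain at the time of the late sample (30 to 100 cells)
- b: suppression gained per 100 CD4 cells (2 to 5 points)
- CD4 standard deviation: 200 cells

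Formulas:

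- Spurious difference in mean CD4 = f × g.
- Standard error of the arm difference in mean CD4 = 200 × √(2/295) = 16.5 cells.
- Shift in the adjusted risk difference ≈ −b × f × g / 100, in percentage points.
- Power, if there is no true difference = Φ[(0.10 + shift)/√(2 × 0.75 × 0.25/295) − 1.96], with the shift as a proportion.

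| f | g | b | CD4 shift (cells) | In SEs | Risk-difference shift (points) | Power |
|---|---|---|---|---|---|---|
| 2% | 30 | 2 | 0.6 | 0.04 | −0.01 | 80% |
| 10% | 50 | 5 | 5 | 0.30 | −0.25 | 78% |
| 25% | 50 | 5 | 12.5 | 0.76 | −0.63 | 75% |
| 50% | 100 | 5 | 50 | 3.04 | −2.5 | 56% |

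A large-sample simulation, using Poisson regression with a log link and marginal standardisation, gave −0.25, −0.61 and −2.4 points for the last three rows, so the approximation is adequate.

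A separate simulation assumed 10% to 30% late samples, on ART in the ART-first arm only, with a gain of 25 to 100 cells and a slope of 3 points per 100 cells. It gave −0.07 to −0.86 points.

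**Reading the range.** Every combination with f up to 10% stays at or below 0.5 points (0.10 × 100 × 5/100 = 0.5). Reaching 1 point or more takes, for example, f = 25% with a 100-cell gain and the steepest slope (1.25 points), or f = 50%. All these shifts apply only if CD4 is actually added to the model.

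**The case against.** The strongest reply is that the design already places CD4 on day 0. The schedule of events (Protocol 6.12) has CD4 only in the screening and enrolment column. Protocol 6.3 lists it among enrolment procedures, ahead of ART initiation in 6.4. The CrAg test depends on CD4 below 200, and a positive CrAg is an exclusion, so the workflow needs the count at enrolment. This stands. It makes the upper end of the assumed range for f implausible and is the main reason the point is minor. It does not remove the SAP rule that accepts a sole late sample.

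A reader might infer that every CD4 drawn on days 1 to 14 in the ART-first arm is an on-treatment value, and that none is in the other arm. The documents do not support that. Same-day ART is an offer, and the SAP treats failure to offer it as an intercurrent event. TB-results-first participants are expected to start within about a week, or on day 0 if TB is diagnosed then, so many of their samples from days 8 to 14 could also be on ART. Only the difference between arms matters, and a calculation that shifts the ART-first arm alone sits toward the upper end.

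It is also fair to say that adjustment is conditional. At f = 10% and a 50-cell gain, the spurious difference is 0.3 standard errors, unlikely by itself to be noticed. However, the SAP's inclusive threshold lowers the bar, and a chance imbalance could bring CD4 into the model anyway.

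**Conclusion.** The point holds as a wording gap with a small expected effect. SAP 3.7 lets a post-randomisation CD4 count as baseline, exposure to ART at that sample differs by arm, and SAP 6.2 lets the value into the primary model. If adjustment is triggered, the shift in the risk difference is probably below 1 percentage point against the 10-point margin. That rests on assumed values for the late share, the CD4 gain and the slope, and on late samples being exceptions, as the schedule implies.

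A reader might infer a threat to the trial's main conclusion or a route to a false claim of non-inferiority. The documents do not support that. If CD4 rises on ART and higher CD4 predicts suppression, the shift runs against ART first. The cost is then accuracy and some power: about 2 points of power in the case with f = 10% and a 50-cell gain. Minor severity; a cheap improvement.

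**What to change.** In SAP 3.7, define baseline CD4, both as a covariate and in the baseline table, as a sample taken no later than the day of randomisation and, where timing is known, before the first ART dose. Apply the same cut-off in both arms.

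Treat later samples as missing baseline CD4, and state how a missing covariate is handled (single imputation or a missing indicator), since SAP 6.3 gives no rule for covariates. Report by arm how many CD4 samples were taken after day 0; this supplies the figure that the documents lack. The 14-day window can be kept as an optional sensitivity analysis. The 28-day rule for prevalent TB serves a different purpose and should stay as it is.

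The cost is one SAP sentence and a date filter. The downside is that a few participants, including any control with a valid pre-ART sample after day 0, lose a usable baseline CD4. If late samples are as rare as the schedule implies, the loss is negligible. The sample size stays at 295 per arm.
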